2.6.1 Primary laboratory predictors (test results considered likely to predict CCB)

Test result	Laboratory test and platform	Likely predictor of CCB
Platelet count	FBC (XE-2100 cell counter)	LOW test result
Multiplate ADP test AUC	Multiplate	LOW test result
Multiplate AA test AUC	Multiplate	LOW test result
Multiplate TRAP test AUC	Multiplate	LOW test result
Multiplate ADR test AUC	Multiplate	LOW test result
ROTEM intem CT	ROTEM	HIGH test result
ROTEM intem alpha	ROTEM	LOW test result
ROTEM intem mcf	ROTEM	LOW test result
ROTEM intem ml	ROTEM	HIGH test result
ROTEM intem maxV	ROTEM	LOW test result
ROTEM intem maxV-t	ROTEM	HIGH test result
ROTEM extem CT	ROTEM	HIGH test result
ROTEM extem alpha	ROTEM	LOW test result
ROTEM extem mcf	ROTEM	LOW test result

STATISTICAL ANALYSIS PLAN

COPTIC: Coagulation and platelet laboratory testing in cardiac surgery
A prognostic study of associations between post-operative test results and subsequent bleeding

ROTEM extem ml	ROTEM	HIGH test result
ROTEM extem a10	ROTEM	LOW test result
ROTEM extem maxV	ROTEM	LOW test result
ROTEM extem maxV-t	ROTEM	HIGH test result
ROTEM fibtem mcf	ROTEM	LOW test result
ROTEM fibtem a10	ROTEM	LOW test result
ROTEM extem mcf - fibtem mcf	ROTEM	LOW test result
ROTEM intem CT - heptem CT	ROTEM	HIGH test result
TEG CK rmin	TEG	HIGH test result
TEG CK angledeg	TEG	LOW test result
TEG CK ma	TEG	LOW test result
TEG CK ly60	TEG	HIGH test result
TEG CK rmin – CKH rmin	TEG	HIGH test result

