2.6.3 Laboratory predictors: timings of test parameters

For each platform, test results have been classified as relevant to a 'rapid' or 'standard' time frame:

Standard Test result	'Early phase' alternative
Multiplate ADP test AUC	ADP test velocity
Multiplate AA test AUC	AA test velocity
Multiplate TRAP test AUC	TRAP test velocity
Multiplate ADR test AUC	ADR test velocity
ROTEM intem CT	n/a
ROTEM intem alpha	n/a
ROTEM intem mcf	Intem A5 or A10
ROTEM intem ml	n/a
ROTEM intem maxV	n/a
ROTEM intem maxV-t	n/a
ROTEM extem CT	n/a
ROTEM extem alpha	n/a
ROTEM extem mcf	Extem A5 or A10
ROTEM extem ml	n/a
ROTEM extem maxV	n/a
ROTEM extem maxV-t	n/a
ROTEM fibtem mcf	Fibtem A5 or A10
ROTEM extem mcf - fibtem mcf	Extem A5-Fibtem A5; Extem A10-Fibtem A10
ROTEM intem CT - heptem CT	n/a
TEG CK rmin	n/a
TEG CK angledeg	n/a
TEG CK ma	CK A30
TEG CK ly60	n/a
TEG CK rmin – CKH rmin	n/a

STATISTICAL ANALYSIS PLAN

COPTIC: Coagulation and platelet laboratory testing in cardiac surgery
A prognostic study of associations between post-operative test results and subsequent bleeding

All other post-operative FBC, Multiplate, ROTEM and TEG test results are considered unlikely to predict CCB.

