 - fit regression models to estimate associations between the results of laboratory tests and the primary clinical outcome, CCB (see [section 5.1](#));
 - develop models that would be informative in predicting risk of CCB according to laboratory test results, both by consideration of these results as continuous measures or as above or below thresholds to be defined using receiver operating characteristic (ROC) analysis.
- A3: In the patient sub-group *aspirin+ P2Y₁₂ blockers*:
- characterise the distribution of time between withdrawal of P2Y₁₂ blocker prior to surgery and time of surgery;
 - fit regression models to estimate the association between the time of withdrawal of P2Y₁₂ blocker (either as a continuous or categorical variable) and the results of the primary laboratory tests (see [section 2.6](#)).
 - fit regression models to estimate the association between the duration of withdrawal of P2Y₁₂ blocker (either as a continuous or categorical variable) and CCB.

Initially the justification for the three separate subgroups would be sought by fitting models for the whole dataset and including interaction terms to formally test for differences between the groups.

The choice of fitting time of withdrawal as a continuous variable or as a category variable in b) and c) above will be based on the i) distribution of times (few discrete values or truly continuous), ii) the functional relationship between the time of withdrawal and the outcome (assessed using fractional polynomials) and iii) interpretability of the findings.

- A4: In all patients:
- fit separate regression models to estimate associations between the results of laboratory tests and the secondary outcomes (see [section 5.2](#));
 - develop models that would be informative in predicting risk of each secondary outcome according to laboratory test results, both by consideration of these results as continuous measures or as above or below thresholds to be defined using receiver operating characteristic (ROC) analysis.

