7.2 Specific analysis procedure

The approach is to evaluate the separate platforms (Multiplate/preop; ROTEM; TEG; Multiplate/postop) individually in the first instance, and then evaluate whether the inclusion of additional platforms would improve this. The reason for considering groups of variables by platform (rather than simply choosing the 'best' subset of variables) is because there is no cost of using extra variables from one platform, but an extra cost of doing a second test. The specific steps are as follows:

- Step 1 Review the prediction achieved by patient characteristics. Define an optimal model based only on "baseline" covariates⁶. There will be a separate model for
- **any CCB** (intra-operative or post-operative) and
 - **post-op CCB** only
- Comment: We expect these models to be consistent with one another, not least because the majority of events (post-op CCPB events) will be common to both models.*
- Step 2 Review of each test platform to obtain the best model for each, including the baseline covariates:
- pre-operative Multiplate in relation to **any CCB** (this model is interesting in its own right, but from a slightly different perspective, i.e. it allows the care team to make a plan to mitigate the risk of CCB or to prepare to manage it)
 - pre-operative Multiplate in relation to **post-op CCB**
 - post-operative Multiplate in relation to **post-op CCB**
 - post-operative ROTEM in relation to **post-op CCB**
 - post-operative TEG in relation to **post-op CCB**
- Comment: Each of these models will consider all variables for the test/timepoint, i.e. consider the test/timepoint as a "package." The first model stands alone for **any CCB**. For **post-op CCB**, this step will identify which of the latter four models is the best platform for predicting CCB, i.e. provides the best prediction. We hypothesise that the best platform will be one of the post-op platforms because the information from these is more 'proximal' to the outcome for these models, i.e. **post-op CCB**.*
- For the best test/timepoint** (assuming there is one best test), we will also investigate whether a model using test variables that are available early (for the test identified as best) performs as well as a model using the standard test variables available at "test completion."

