7.3 Model fitting

Models will be fitted first for the standard time frame. Then, models will be fitted for the rapid time frame (see [Table 2.6.3](#)), testing whether this results in a “significant” deterioration in prediction. Comparing rapid and standard time frames is interesting because there may be a trade-off between potential benefits of earlier decision making (e.g. allows definitive treatment to be provided more quickly, thereby preventing blood loss) vs. potential harms (e.g. somewhat less good prediction).

The contribution of all of these baseline characteristics to the prediction of CCB were incorporated into a single score which was forced into models of laboratory predictors with a coefficient of 1.00 in order to enable comparisons between different models based on the various laboratory test platforms.

All laboratory measures from a platform were included for each model, with multivariable fractional polynomial techniques used to investigate the linearity of terms. All transformations and centering found to improve the fit of the models were implemented. Backward elimination was undertaken to select the final models with a threshold of inclusion of 0.05 and exclusion of 0.10. Initial models only considered the standard test results (see Table 2); subsequently the ‘early phase’ alternatives were considered for any terms that significantly contributed to the model.

The following models were constructed:

- **Model 2A:** pre-operative Multiplate in relation to **any CCB**
- **Model 2B:** pre-operative Multiplate in relation to **post-op CCB**
- **Model 2C:** post-operative Multiplate in relation to **post-op CCB**
- **Model 2D:** post-operative ROTEM in relation to **post-op CCB**
- **Model 2E:** post-operative TEG in relation to **post-op CCB**

Each model was then compared to a baseline model containing only the baseline characteristics in order to evaluate the contribution of the selected laboratory test results to the prediction of CCB. These are presented as receiver operating characteristic (ROC) curves.

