7.4.3 Analysis models

All outcomes listed in the study protocol will be presented as per the template tables [Table T7 to T8](#). General methods of presentation are outlined below.

⁷ i.e. factors associated with the both the laboratory test result(s) (exposure) and the outcome, unbalanced across the groups and not an intermediary step in the causal pathway from the exposure to outcome

The primary outcome (CCB) and secondary outcomes (any RBC transfusions > 4 units RBC transfusion, non-routine pro-haemostatic treatments, death, MI, any stroke, renal failure, AKI and infections during hospital admission) are all binary data.

These binary outcomes will be presented as numbers and percentages of patients. The association between laboratory test results and outcome will be quantified using logistic regression for binary data. Estimates will be presented as unadjusted and adjusted odds ratios (OR) and 95% confidence intervals (95% CI). For these binary outcomes analyses will only be performed if more than ten patients in total experience the outcome.

The sensitivity and specificity of laboratory test results to predict the outcome will be described for different thresholds and laboratory tests will be compared using the area under the receiver operating characteristic (ROC) curve.

The association between time of withdrawal of P2Y₁₂ blocker and laboratory test results will be described using linear regression.

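### Platform models are selected and ranked in the same patients with no internal validation, which tilts close comparisons towards ROTEM and could seriously inflate rare-outcome models

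*SAP*

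**What the plan says.** **Model building (SAP 7.3).** The starting pool is wide: "All laboratory measures from a platform were included for each model". Multivariable fractional polynomials set the shapes, and "All transformations and centering found to improve the fit of the models were implemented". Then "Backward elimination was undertaken to select the final models with a threshold of inclusion of 0.05 and exclusion of 0.10". The initial models are confined to the standard test results. Early-phase alternatives come in later, for terms that contributed. Baseline characteristics enter as one score with its coefficient fixed at 1.00.

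**Choice of platform (7.2, Step 2).** Four models for post-operative CCB are set against each other: pre-operative Multiplate, and post-operative Multiplate, ROTEM and TEG. The comment says "this step will identify which of the latter four models is the best platform for predicting CCB". Steps 3 and 4 and the early-versus-standard comparison all start from the winner.

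**Measure of prediction.** Step 2 names none. Section 7.4.3 compares laboratory tests by area under the ROC curve, and 7.3 presents ROC curves against the baseline model. Section 7 (A1, A2, A4) also uses test results as "above or below thresholds to be defined using receiver operating characteristic (ROC) analysis".

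**Secondary outcomes.** A4 plans prediction models for each one. Section 7.4.3 sets a minimum for binary outcomes: "analyses will only be performed if more than ten patients in total experience the outcome".

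**Validation.** No section mentions bootstrap, cross-validation, a hold-out sample, shrinkage or optimism correction. Section 7.4, on avoiding bias, deals with recruitment and blinding. Section 7.4.10 leaves multiplicity adjustment open.

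**The concern.** A model whose terms and shapes were chosen in one set of patients predicts those patients better than it will predict new ones. This optimism grows with the number of candidates tried and shrinks with the number of events. Section 7.2 reasons that extra variables from one platform cost nothing. That is true of testing cost but not of over-fitting.

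Because the pools differ three- to four-fold, the optimism differs between platforms, and the comparison in Step 2 is not on equal terms. A platform could be named best partly because it reports more parameters, and every later step would inherit that choice. For rare secondary outcomes the danger is different: a model with no real predictive value could show an AUC that looks useful.

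**Working it through.** **Candidate counts (2.6.1, 2.6.3).** The standard column of 2.6.3 lists:
- ROTEM 15: six intem, six extem, one fibtem and two differences, one of them "ROTEM intem CT - heptem CT"
- TEG 5
- Multiplate 4

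The other ROTEM difference, extem mcf minus fibtem mcf, is an exact linear combination of two listed candidates. There are therefore 14 independent linear terms, and all three cannot be fitted together as linear terms.

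**Chance survival at the 0.10 removal threshold.** With k independent noise candidates, the expected number kept is 0.10k and P(at least one kept) = 1 - 0.9^k.
- ROTEM, k = 15: 1.5 expected; 1 - 0.9^15 = 0.794 (k = 14: 0.771)
- TEG, k = 5: 0.5 expected; 1 - 0.9^5 = 0.410
- Multiplate, k = 4: 0.4 expected; 1 - 0.9^4 = 0.344

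**Simulated optimism and ranking.** The SAP gives neither an event rate nor a number analysed, so these are assumed around its planned size of 2400 (section 3.1). Laboratory variables were pure noise with pairwise correlation 0.3. The baseline score was an offset with coefficient 1, and elimination was at p > 0.10. There were 100 replicates per row. Optimism is the AUC in the fitted patients minus the AUC in 20,000 new ones.

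| Patients / events | ROTEM (15) | TEG (5) | Multiplate (4) | ROTEM ranked first |
|---|---|---|---|---|
| 2400 / 960 | 0.005 | 0.001 | 0.001 | 61% |
| 2400 / 480 | 0.005 | 0.001 | 0.001 | 59% |
| 2400 / 120 | 0.020 | 0.001 | -0.001 | 81% |
| 1000 / 200 | 0.019 | 0.007 | 0.007 | 61% |
| 2400 / 25 | 0.070 | 0.015 | 0.011 | 65% |
| 2400 / 11 | 0.127 | 0.053 | 0.045 | 58% |

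With three platforms on equal terms, each would rank first in one third of runs. The Monte Carlo standard error of a 60% share is sqrt(0.6 × 0.4 / 100) = 0.05. When each platform was given one equal true predictor (log odds ratio 0.15), ROTEM still ranked first in 49% (2400 patients, 480 events) and 58% (1000 patients, 200 events).

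The simulation leaves out fractional polynomials and estimation of the baseline score, so it probably understates optimism. It also compares three platforms rather than the four models in Step 2.

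**Does correction matter?** In a further null run (1000 patients, 20% events, 150 replicates), ROTEM ranked first in 72% on apparent AUC. After bootstrapping the elimination (30 resamples) it ranked first in 7%. The corrected share falls below one third because, when every candidate is noise, the smaller models do predict new patients better.

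**Event floor.** More than ten means 11 events, which gives 11/15 = 0.73 events per ROTEM candidate, 11/5 = 2.2 for TEG and 11/4 = 2.75 for Multiplate.

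**The case against.** **Size for the primary outcome.** The strongest counter-argument is that CCB may well have several hundred events, and then the inflation is a few thousandths of AUC even in the worst case of no true signal. That can reverse a ranking only when platforms are nearly tied. This stands and limits the point.

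**Measure.** A reader might infer that the plan ranks platforms on apparent AUC. It does not say so. AUC is inferred from 7.4.3 and from the ROC curves in 7.3, and 7.4.4 prefers likelihood ratio tests for hypothesis testing. What remains is that any measure computed in the fitting patients, without correction, has the same weakness.

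**Candidate count.** A reader might count 17 ROTEM candidates, because 2.6.1 also lists "ROTEM extem a10" and the fibtem equivalent. Section 7.3 limits the initial models to standard results, and 2.6.3 places the A10 values among the early-phase alternatives, so 15 is the right count.

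**Rare outcomes.** It is tempting to picture the 12 baseline covariates of the 7.2 footnote entered together with the laboratory variables on 11 events. Fourteen pure-noise predictors fitted at once to 11 events give a mean apparent AUC of 0.79 against a true 0.50. The documents plan no such fit: 7.3 uses a single fixed score followed by elimination, and 7.4.2 admits confounders selectively. The figures in the table are nearer to the stated procedure.

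**The floor itself.** The more-than-ten rule covers every binary analysis, including unadjusted odds ratios. It is not a statement about how large a model may be, and simply replacing it would do harm.

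**Cut-points.** For one marker with AUC about 0.65 and 400 to 450 events, optimism is about 0.02 in sensitivity and under 0.01 in specificity. It becomes large only near the event floor.

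**Conclusion.** The point holds with limited size. The SAP fixes a fully data-driven procedure and a comparison of its results, and provides no correction for optimism.

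For CCB, the distortion is in the ranking more than in the AUC values. ROTEM optimism is about 0.005 with 480 to 960 events and about 0.02 with 120 to 200. The documents do not support saying that the CCB results would be badly inflated, or that ROTEM would win against a clearly better platform.

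For secondary outcomes near 11 events the inflation would be material: about 0.13 for ROTEM with 15 candidates (0.15 if 17 were used), and about 0.03 to 0.05 for TEG and Multiplate across two simulations. This assumes that the selection described in 7.3 for the CCB models is also used under A4, which is an inference.

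All simulated sizes rest on assumed event counts. The absence of internal validation and the unequal pools do not depend on those assumptions.

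**What to change.** **Section 7.3.** State that platforms are ranked on optimism-corrected AUC. Obtain it from a bootstrap (for example 500 resamples) that repeats the whole procedure: baseline score, fractional polynomials, elimination and cut-point choice. Use patients with results on all platforms being compared. Report corrected AUC, corrected sensitivity and specificity at the chosen cut-points, and confidence intervals for AUC differences.

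**Section 7.4.3.** Keep more than ten patients as the floor for descriptive and single-predictor analyses. Add a separate rule for secondary-outcome prediction models: build a multivariable model only when events are adequate for the number of candidate parameters. State the limit in advance and define how fractional-polynomial terms are counted. Below the limit, report one laboratory variable at a time by Firth-penalised logistic regression and develop no prediction model.

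Do not apply this limit to the primary CCB models, which would rely on the bootstrap. As an illustration, ten events per parameter would require 15 × 2 × 10 = 300 events for ROTEM with first-degree terms (2 parameters each), or 15 × 4 × 10 = 600 with second-degree terms (4 each). That could bar the main ROTEM model.

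**Cost.** No new data are needed, so the change remains possible although 7.3 is written in the past tense. It takes some computing time and SAP wording. Reported AUCs will be slightly lower, and some rare-outcome prediction models will be dropped.

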2.7 Other predictors and confounders

The role of other possible predictors and potential confounders will be investigated. These factors will be evaluated for association with the laboratory test results and association with the primary and secondary outcomes and will include age, sex, diabetes, type of surgery, operation urgency, pre-operative kidney function (estimated Glomerular Filtration Rate; eGFR) and pre-operative HCT. Post-operative platelet count will also be included in all models.

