⁶ These are: age, sex, diabetic status (n/y), cardiac procedure (CABG only, CABG + valve, valve alone, other), operative priority (elective, urgent), eGFR, preoperative HCT, treatment group, time since withdrawal (anti-platelet group), body mass index (BMI), preoperative platelet function and participation in another clinical study.

- Step 3 Test whether the addition of one of the other (post-operative) platforms improves this best model for **post-op CCB**. In practice, this is likely to be a test of whether Multiplate-post improves prediction compared to either ROTEM or TEG (or, adding ROTEM or TEG to Multiplate-post, since ROTEM and TEG are assessing similar mechanisms and Multiplate is assessing different ones). The combination of ROTEM and TEG together will not be considered.
- For the test/timepoint** added at Step 3 (assuming that there is one), we will also investigate whether a model using test variables that are available early (for the test/timepoint added at Step 3) performs as well as a model using the standard test variables available at “test completion.”
- Step 4 Test whether the addition of the pre-operative Multiplate platform improves the model identified in Stage 3.
- If Multiplate-pre** is added at Step 4, we will also investigate whether a model using test variables that are available early for Multiplate-pre performs as well as a model using the standard test variables available at “test completion.”

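### Sections 2.7 and 7.3 do not agree on whether post-operative platelet count is in the platform models; if it is, the AUC gain credited to Multiplate, ROTEM or TEG includes the count's own prediction

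*SAP*

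**What the plan says.** Section 2.7 lists the other predictors and confounders and closes with: "Post-operative platelet count will also be included in all models". Section 2.6.1 lists platelet count as a primary laboratory predictor, with a low value expected to predict clinical concern about bleeding (CCB). Its source there is the full blood count analyser, so it is not a Multiplate, ROTEM or TEG measure.

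Step 1 of section 7.2 reads "Review the prediction achieved by patient characteristics. Define an optimal model based only on" baseline covariates. Footnote 6 lists these. The list ends with "body mass index (BMI), preoperative platelet function and participation in another clinical study" and contains no post-operative count.

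In section 7.3 the baseline characteristics are combined into one score, "forced into models of laboratory predictors with a coefficient of 1.00". On the laboratory side, "All laboratory measures from a platform were included for each model". The comparison is then fixed: "Each model was then compared to a baseline model containing only the baseline characteristics in order to evaluate the contribution" of the selected laboratory tests to the prediction of CCB. It is shown as ROC curves, and section 7.4.3 compares tests by the area under the curve (AUC).

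**The concern.** Section 7.3 does not mention the post-operative count, and section 2.7 does not limit what it means by all models. An analyst who follows both literally puts the count into Models 2C, 2D and 2E and leaves it out of the comparator. The two models then differ by the platform's tests and the count together, yet the difference is labelled as the contribution of the tests.

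The SAP itself expects a low count to predict CCB. A platform that adds little beyond the count could therefore be reported as improving prediction. Section 7.2 organises the analysis by platform because a second test carries a cost, so the size of each test's contribution matters to the study's message. No ROC comparison against baseline plus count is planned in 7.2 or 7.3.

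**Working it through.** The SAP states no AUC, odds ratio, correlation or CCB rate for these models, so there is no figure to reproduce. The check is one of model structure, followed by an illustration on assumed inputs.

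**Step 1: possible readings.** Let B be the baseline score, C the post-operative platelet count and T the platform tests.

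| Reading | Platform model | Comparator | Fits 2.7? | Fits 7.3 and footnote 6? |
|---|---|---|---|---|
| A | B + C + T | B | In the platform model only | Comparator yes; C is not mentioned for the platform model |
| B | B + T | B | No | Yes |
| C | B + C + T | B + C | Yes | No: the comparator holds baseline characteristics only |

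No reading satisfies both sections in full. A and B keep the 7.3 comparator; C does not.

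**Step 2: what each reading measures.** Under A the reported gain splits exactly:

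AUC(B+C+T) − AUC(B) = [AUC(B+C+T) − AUC(B+C)] + [AUC(B+C) − AUC(B)]

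The first bracket is what the platform adds beyond the count. The second is the count alone. Under B the gain is AUC(B+T) − AUC(B): no term for C is present, but T carries whatever information it shares with C.

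**Step 3: illustration.** All inputs are assumptions, with 200,000 simulated patients per scenario:

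logit P(CCB) = a + b + ln(OR_C)·x + ln(OR_T)·w, with w = ρx + √(1−ρ²)·e

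- b is the baseline score: SD 0.7, coefficient fixed at 1.00, independent of x. This gives a baseline AUC of about 0.66 to 0.68.
- x is the standardised count, signed so that a higher value means more risk. OR_C per SD is 1.2, 1.5 or 1.8.
- w is a platform test, with OR_T per SD given the count of 1.0 (nothing added) or 1.3.
- ρ is 0.3 or 0.6, and the CCB rate is 20% or 35%.

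Three of the 24 scenarios:

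| OR_C, OR_T, ρ, CCB rate | B | B+C | B+T | B+C+T | Gain, reading A | Gain, reading B | Gain beyond count |
|---|---|---|---|---|---|---|---|
| 1.2, 1.3, 0.3, 20% | 0.680 | 0.692 | 0.698 | 0.703 | 0.023 | 0.018 | 0.011 |
| 1.5, 1.0, 0.6, 35% | 0.678 | 0.707 | 0.689 | 0.707 | 0.029 | 0.011 | 0.000 |
| 1.8, 1.3, 0.6, 20% | 0.669 | 0.746 | 0.723 | 0.751 | 0.082 | 0.054 | 0.005 |

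The last row shows the split in Step 2: 0.751 − 0.669 = 0.082, of which 0.746 − 0.669 = 0.077 is the count and 0.751 − 0.746 = 0.005 is the platform.

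Ranges over all scenarios:

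- Test adding nothing beyond the count: 0.006 to 0.054 under A; 0.000 to 0.006 (ρ = 0.3) and 0.002 to 0.022 (ρ = 0.6) under B; 0.000 beyond the count.
- Test with its own OR of 1.3: 0.023 to 0.085 under A; 0.017 to 0.057 under B; 0.005 to 0.011 beyond the count.

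**Step 4: dependence on the assumptions.** A second simulation (400,000 patients, baseline AUC 0.67, log ORs of count and test summing to 0.7, correlation 0.4 to 0.7) gives 0.054 to 0.064 under A, 0.027 to 0.057 under B and 0.003 to 0.020 beyond the count. If the baseline score is itself correlated 0.4 with the count, A falls to about 0.041 to 0.046 and B to about 0.018 to 0.041. With smaller log ORs (0.18 and 0.26), A is 0.021 to 0.022 and B is 0.017 to 0.020. The direction is stable; the size is not.

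**The case against.** The best defence is one of scope. The sentence in 2.7 sits among confounders, and 7.4.2 refers back to 2.7 for adjustment, so it may govern only the adjusted odds ratios. Sections 7.2 and 7.3 describe a platform prediction procedure that the amendment log places in version 3.0. On that view the count is in neither model, and the gain over baseline is a legitimate quantity: what running the platform as a package adds to patient characteristics. This stands as a possible reading. It is nowhere stated, though, and 7.4.2 names only age and sex as entering all final models, so the reach of 2.7 is left open even for the association models.

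The opening of section 7 also plans models in which laboratory parameters are adjusted for each other. That may yield count-adjusted associations, but it does not alter the ROC comparator in 7.3.

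Three stronger inferences should be resisted:

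- A reader might conclude that the reported gain certainly includes the count. That needs the count in the platform model only, and 7.3 never says so.
- A reader might conclude that the choice of best platform is compromised. Step 2 compares platforms with each other and Step 3 tests additions to the best model. If the count is common to 2C, 2D and 2E, their ranking is less affected than the gain over baseline.
- A reader might argue that the count is already in hand at the bedside, so only the gain beyond it matters. The SAP shows only that full blood count results are linked in the research dataset (4.2, Step 5), and 7.4 says laboratory results are not released to treating clinicians.

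**Conclusion.** The concern holds as an unreconciled specification with a conditional consequence. With the count in the platform models and the comparator as written, the gain attributed to the platform mixes two sources. With the count in neither, the gain is valid as gain over patient characteristics but is silent on what the platform adds beyond the count; the ranking could also move if platforms correlate differently with the count.

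The size cannot be derived from the SAP. The AUC differences above rest wholly on assumed effects, correlations and CCB rates, and mostly on a baseline score independent of the count. They show that the misattribution can be several times the platform's own contribution, not that it is. The point concerns Models 2C to 2E. For the pre-operative Models 2A and 2B a post-operative count would not be available at the time of prediction, which is a further reason to define what 2.7 covers. It should be settled before the gains are reported.

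**What to change.** 1. Reconcile 2.7 with 7.3 and footnote 6 by naming the models that hold the post-operative platelet count, and keep the same count terms on both sides of every comparison.
2. For Models 2C, 2D and 2E, add a reference model of baseline score plus post-operative platelet count. Report the AUC difference and the likelihood ratio test of baseline plus count plus platform against it, in the same patients.
3. Keep the baseline-only comparison beside it, with the count in neither model, labelled as the gain over patient characteristics.

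The cost is a change of wording and one extra reference model, on data already being linked. Section 7.3 is written in the past tense, so the models may already have been fitted; if so, this is an added analysis for an SAP amendment. The reported gain for each platform will probably be smaller.
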